## **Objective 2:**

Quantitative Analysis of Caregiver Survey Data - The primary comparison of interest will be the change in outcomes from the baseline survey to the follow survey between VD-HCBS Caregivers and VA CARES participants. Before testing for change over time, we will examine the frequency distributions for all study variables and appropriate transformations will be carried out whenever violations of normality are determined. Descriptive statistics and bivariate correlations will be computed. Each variable will be tested for leptokurtosis to ensure that there is a sufficient range of scores. Variables found to be significantly leptokurtic will be converted into dichotomous outcomes.

An important issue for longitudinal follow-up analyses is the problem of missing data. Data may be missing for one of two reasons: 1) the Veteran of a Caregiver who participated in baseline is no longer receiving VD-HCBS at the 6-month follow-up period; 2) a Caregiver participant is lost to follow-up because of non-participation. In order to avoid biasing the result by including only Caregivers who complete both surveys, we will first examine whether there are indications that the data are missing completely at random. Specifically, we will compare baseline scores for Caregivers that complete both surveys to those that did not complete the follow-up survey. If no significant differences are observed between completers and those that "dropped out" on the baseline variables, then we will proceed with data analysis of the Caregivers who completed both rounds of the survey. However, if we determine that the data are missing at random, then we will impute the missing data using a multiple imputation technique. If necessary, we will perform sensitivity analysis to examine the plausibility of the missing at random assumption using a pattern mixture approach.

In order to compare the VD-HCBS Caregivers to the control group of Caregivers from the VA CARES evaluation (non-approved Caregivers, n=66), we will attempt to identify VD-HCBS Caregivers that are similar to the control group participants in terms of baseline survey variables. Identifying matching individuals on the entire set of covariates may be complex, so we will rely on the propensity score, a technique used in non-randomized studies to balance groups based on observed differences. Because the number of participants in our control group is significantly smaller than the one expected in VD-HCBS, we will use matching with replacement in which controls can be used multiple times to match within a specified caliper. Caregivers in VD-HCBS that will not have a matching VA CARES within a caliper will be removed from the analysis, because the positivity assumption does not seem to be valid for them. This procedure will include many Caregivers in VD-HCBS, which will improve the precision of point estimates in this group while maintaining only VD-HCBS Caregivers that are relatively similar to control Caregivers. Having a large number of Caregivers from VD-HCBS increases the power of the study, but it is dominated by the precision in the control group. To estimate the propensity score, we will use a logistic regression model  $P(C_i|X_i) = \frac{\exp(\beta'X_i)}{1 + \exp(\beta'X_i)}$ , where Ci is indicator variable for whether Caregiver i is from the VD-HCBS program or the control group, and Xi are the set of baseline covariates for caregiver i. Following the propensity score calculation, we will match Caregivers in the control group to VD-HCBS Caregivers using the estimated propensity scores. We will then examine whether the distributions of the baseline covariates and second order interactions are similar across the two groups. Differences in distributions will be examined graphically and via appropriate statistical tests. If some variables are found to differ between groups, we will update the propensity score model with higher order interactions. We will repeat this procedure until balance is obtained on all baseline variables and their interactions. 40

Because the matching is not exact, there might be minor imbalances between the covariates among Caregivers in VD-HCBS and the control group. To address these minor imbalances, we will rely on general linear regression models to estimate differences in the outcomes between Caregivers who are participating in the VD-HCBS program and those who were part of the VA-CARES evaluation. For continuous outcomes, we will use multiple linear regression  $Y_i = X_i\beta + \tau C_i + \varepsilon_i$ , where Yi is the outcome for Caregiver i, Xi are the covariates, Ci is an indicator variable for Control/VD-HDBS,  $\tau$  is the treatment effect and  $\varepsilon_i \sim N(0, \sigma^2)$ . For the ordinal variable, we will use the proportional odds model  $logit(Y_i < j) = \alpha_j + X_i\beta + \tau C_i$ , where  $\alpha_j$  is the log-odds of the outcome variable j, and the rest of the variables are as previously described. To obtain interval estimates we will use either the variance estimates provided by Abadie & Imbens or the bootstrap procedure.

Dependent Variables – We will examine Caregivers' perceived financial strain, CESD-10 score (screener for depressive symptoms), burden, self-reported health, and positive aspects of caregiving as described in the table below.

Dependent Variables for Objective 2								
Measures of	Measurement							

Independent Variables-To examine improvements in the various outcomes, the models will examine Veteran and Caregiver characteristics that may be related to improvement as well as their baseline values on each of the measures of interest. Most of these characteristics will be measured during baseline surveys of

Item Impact on Finances subscale from the Caregiver Reaction								
Assessment								
es range 3-15 where higher scores indicate higher strain.								
enter for Epidemiologic Studies Depression 10 item Scale (CE SD 10).								
cores range 0-30 where higher scores indicate more depressive								
ymptoms.								
arlt Caregiver Burden. Defined as the level of stress felt by a								
Caregiver. The scale covers the areas most often mentioned by								
Caregivers as problems, including health, psychological well-being,								
nances, social life, and the relationship shared by the Caregiver and								
are recipient.								
cores range 0-48 where higher scores indicate higher burden.								
ingle item from the Health and Retirement Study (2012)								
esponses are "Poor", "Fair", "Good", "Very Good" or "Excellent"								
line items assessing positive aspects of caregiving as captured by								
arlow and colleagues' reliable and well-validated measure.								
cores range from 9-45 where higher indicates more positive aspects								
f caregiving experienced.								

Caregivers and a few will be drawn from the Veteran Assessment Data. For example, the models will include Veterans' demographic and health/function characteristics, month of enrollment, and the Veterans' monthly budget amount. We will also examine Caregiver characteristics such as their relationship with the Veteran, whether or not the Caregiver was employed, lived with the care recipient, as well as their age, sex, race, education, marital status, and whether or not there are dependent children in the household.

Power-

Without any adjustment for covariates and assuming that the standard error is equal to

Estimated Power for Aim 2 Caregiver Analysis by Effect Size and Number of Surveys											
VD- HCBS	5120 0110	Effect Size									
Caregiver Surveys	3 pts	3.5 pts	4 pts	4.5 pts							
(n)	P13	pts	pt3	pts							
500	56%	70%	80%	89%							
1,000	58%	71%	82%	90%							
2,000	59%	73%	83%	91%							

10 (the observed standard deviation on the Positive Aspects of Caregiving Scale in the non-approved "control group" from the VA Cares evaluation, n=55 respondents for this scale), we should have over 80% power to identify a difference of 4 points on the Positive Aspects of Caregiving Scale (range 9-45) with approximately 1,000 Caregivers in VD-HCBS (see Table 4). If we used a

different control group, (i.e., the approved Caregivers in the VA CARES evaluation, n=92 respondents), we can identify a 3.1 point difference on this scale. Using regression adjustments, we are expecting to be able to identify even smaller effects. Therefore, we expect to have a large enough sample size to detect a meaningful difference in at least one of the outcomes for this objective

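### Objective 2 lets the observed distributions choose the analysis scale of the caregiver outcomes and does not protect the raw-point difference, the only effect that is powered

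*Combined protocol and SAP*

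**What the plan says.** All of this is in section 7.0 Data Analysis, Objective 2, of the combined protocol and SAP.

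- **Endpoint.** "The primary comparison of interest will be the change in outcomes from the baseline survey to the follow"-up survey, VD-HCBS caregivers against VA CARES participants.
- **Scale rules, applied before change is tested.** The team states that "we will examine the frequency distributions for all study variables" and that "appropriate transformations will be carried out whenever violations of normality are determined". It adds: "Variables found to be significantly leptokurtic will be converted into dichotomous outcomes". No normality test, threshold, transformation, back-transformation or cut-point is given.
- **Outcomes.** Four multi-item scores: financial strain (3-15), CESD-10 (0-30), burden (0-48) and positive aspects of caregiving (9-45). Self-reported health is a single item with five ordered responses.
- **Model.** "For continuous outcomes, we will use multiple linear regression", with normally distributed errors and a treatment effect tau that has no stated unit. The ordinal outcome gets a proportional odds model. Intervals come from Abadie-Imbens variances or a bootstrap. Baseline values of the measures are among the covariates.
- **Power.** "we should have over 80% power to identify a difference of 4 points on the Positive Aspects of Caregiving Scale", with about 1,000 VD-HCBS caregivers, 55 controls and SD 10. No other outcome is powered.

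**The concern.** The power paragraph describes a difference in mean points. The rules that come before the analysis allow the same score to be replaced by a transformed or a two-category version, depending on how the data look. The plan does not link the two.

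Three things make this more than a matter of wording.

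- The check is made on the variables themselves, whereas the regression model places normality on the error term. A skewed or flat raw score does not by itself violate that model.
- The planned interval methods do not require normal scores, so the transformation buys little.
- A difference in mean log or root scores is a different hypothesis from a difference in mean points. Two groups with the same mean score but different spread have different mean logs. The groups here are not randomised and come from different programs, so unequal spread is plausible, and propensity matching does not equalise outcome variances.

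At stake are the meaning of the program effect, its link to the stated power, and the room left for choosing the scale after seeing the data.

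**Working it through.** **1. Reproduce the stated power.** Inputs from the Power paragraph: difference 4, SD 10, 55 controls, 1,000 VD-HCBS caregivers. Alpha is not stated; two-sided 0.05 is assumed.

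- SE = 10 × √(1/55 + 1/1000) = 1.385
- Power = Φ(4/1.385 − 1.960) = Φ(0.928) = 82.3%, against 82% in the table.

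All 12 cells of the table reproduce within 1 percentage point. One-sided 0.05 would give 89.3% for this cell and 66 controls would give 88.2%, so neither was used. The arithmetic is sound, and it describes a raw-score comparison.

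**2. Would the rule be triggered?** The score means are not in the documents; 27, 30 and 33 are assumed. Integer scores on 9-45 with SD 10 (a 36-point range) were simulated, 400 data sets per setting. Shapiro-Wilk rejects normality in 100% of data sets at n = 500 and at n = 1,000, for both rounded normal and rounded beta shapes.

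Milder assumed shapes depend on the test. At n = 1,000:

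| Assumed score | Shapiro-Wilk | Jarque-Bera |
|---|---|---|
| 9-45, mean 27, SD 6 | 100% | 3% |
| 0-48, mean 20, SD 9 | 100% | 18% |

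Sample size also drives the outcome. A sample skewness is significant at 5% beyond about 1.96 × √(6/n): 0.15 at n = 1,000 and 0.65 at n = 55. In the rounded normal shapes the leptokurtosis rule was triggered in 0% of samples of 1,000, because their tails are light.

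**3. What a transformed contrast measures.** Four raw points are ln(19/15) = 0.236 log units at a score of 15, but ln(44/40) = 0.095 at a score of 40. No single power figure in points carries over.

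**4. What a dichotomised contrast would do.** For an assumed median split of a normal score with SD 10, a 4-point shift becomes 50.0% against Φ(0.4) = 65.5%. Power with 1,000 and 55 caregivers is then 64.5%.

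**5. False positives for a difference in mean points.** Beta-shaped integer scores on 0-30, both means 10 (so no difference in points), 1,000 VD-HCBS caregivers and 55 controls, Welch test at two-sided 5%, 3,000 to 4,000 data sets per setting. Means and SDs are assumed.

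| SD control / VD-HCBS | Raw | Square root | log(x+1) |
|---|---|---|---|
| 6 / 4.5 | 5-6% | 8% | 14% |
| 5 / 6 | 5-6% | 8% | 15-16% |
| 5 / 7 | 5-6% | 20-21% | 47-48% |
| 6 / 5.5 | about 5% | 5% | 6% |
| equal | about 5% | no inflation | no inflation |

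The raw scores have skewness of about +0.4 to +0.6. The square root brings it to about −0.2. The log takes it to about −0.7 to −0.8, an over-correction.

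**The case against.** The strongest case against has four parts.

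- **The rule is conditional.** It speaks of looking at frequency distributions and names no significance test. A reader might infer that with about 1,000 caregivers the tested endpoint is bound to leave the points scale. The documents do not support that: visual review could leave every score raw, and some formal tests would pass milder shapes. About 1,000 is also one planning row, next to 500 and 2,000. What stands is that the result depends on a test or judgement that the plan does not name.
- **Only one outcome is powered in points.** It would be wrong to say that the Objective 2 outcomes as a whole are powered that way, or that tau is stated in points. Self-reported health is ordinal and lies outside this point.
- **The larger error rates use a poor transformation.** The 14-47% range comes from log(x+1), which worsens the skewness. A transformation that deserves to be called appropriate gives about 8-20%, and only when the spreads differ by more than a little. The simulation is also an unmatched comparison at one time, whereas the plan matches, adjusts and analyses change. The figures show the mechanism; they do not predict the error rate of the planned analysis.
- **Transforming skewed scores before a normal-error model is conventional.** That is fair. But the model's assumption concerns errors, the planned intervals do not rely on it, and convention does not remove the need to fix the primary scale in advance.

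**Conclusion.** The concern holds as a gap in specification. The analysis scale of the four multi-item outcomes is driven by the data, through two rules without stated criteria, and no section keeps the raw-point difference as primary even though it is the only effect powered. The power figure itself is correct (82.3% against 82%).

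The size depends on what the rules trigger. If scores stay raw, nothing changes. If a score is transformed, the contrast leaves the points scale. With equal raw means, the false-positive rate for a difference in mean points is then about 5% when spreads are equal or nearly so, and about 8-20% after a square root under the larger SD differences tried. If a score is split at the median, power for the same 4-point shift is about 64.5%.

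These figures rest on two-sided alpha of 0.05, assumed means, assumed SDs for every scale except positive aspects of caregiving, and assumed bounded shapes. Like the plan, the 82% takes SD 10 as the SD of the analysed quantity.

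**What to change.** In the Objective 2 quantitative analysis text, replace both scale-changing rules with wording to this effect: the four multi-item scales (3-15, 0-30, 0-48, 9-45) are analysed primarily in their original points, using the baseline adjustment and the Abadie-Imbens or bootstrap intervals already in the plan. Transformation for non-normality and dichotomisation for leptokurtosis are limited to labelled sensitivity analyses, with the transformation, the cut-point and the trigger (preferably based on model residuals) named in advance. Self-reported health stays under the proportional odds model.

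Both rules must be changed together. If the dichotomisation rule were left, it would contradict a commitment to points.

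The cost is a few sentences, with no new data, and the stated 82% power is unaffected. The downside is some possible loss of efficiency if a score proves very skewed.

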## **Objective 2**

The second objective of this evaluation is to understand the effect of the VD-HCBS program on Caregivers' well-being. This will be done using telephone surveys with caregivers. Each Caregiver will participate in two 20-minute phone surveys held 12 months apart. These calls will not be audio recorded, but caregiver responses will be entered into the project database using a unique coded ID. A crosswalk to the database will be maintained separately in a restricted access folder on the Providence VA server. We will examine the outcomes for Caregivers of Veterans enrolled in the VD-HCBS program and compare this to a control group of Caregivers using data previously collected as part of the VA CARES evaluation.

Data for the outcomes for Caregivers of Veterans enrolled in the VD-HCBS program will be collected via telephone survey and data from the control group will be acquired following an approved Data Use Agreement with the VA Office of Geriatrics and Extended Care. We will test our working hypothesis through analysis of the telephone surveys and compare them to Caregivers who participated in a previous partnered evaluation of the Caregiver Support Program. With the documented relationship between Caregiver burden, stress, strain and quality of life and the ability for the care-recipient to remain in the home, it is imperative to understand the impact on caregivers as part of the causal chain of program impact for Veterans. When the proposed studies from this objective are completed, it is our expectation that the impact of the VD-HCBS program on Veterans' Caregivers will be better understood. Our proposal for analysis of the Caregiver Survey Data is describe in Section 6.0 (objective 2).

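### Two significance pre-tests steer the Objective 2 analysis: a kurtosis test can turn a scale score into a yes/no outcome at an unstated cut, and a non-significant baseline comparison leads to completers only with no required check

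*Combined protocol and SAP*

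**What the plan says.** Both rules are in the combined protocol and SAP, section 7.0, Objective 2, under the quantitative analysis of caregiver survey data.

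*Distribution rule.* Variables that violate normality are to be transformed. Later in the same paragraph every variable is tested for leptokurtosis, with the stated aim of securing an adequate spread of scores, and "Variables found to be significantly leptokurtic will be converted into dichotomous outcomes". The test, its level, the group and time point it applies to, and the cut are not given. The models that follow are linear regression for continuous outcomes and, for self-rated health, "For the ordinal variable, we will use the proportional odds model".

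*Missing-data rule.* The first listed reason for loss is that "the Veteran of a Caregiver who participated in baseline is no longer receiving VD-HCBS"; the second is survey non-participation. Baseline scores of completers and drop-outs are compared. If nothing is significant, "then we will proceed with data analysis of the Caregivers who completed both rounds of the survey". Otherwise, "if we determine that the data are missing at random, then we will impute the missing data". The paragraph ends: "If necessary, we will perform sensitivity analysis to examine the plausibility of the missing at random assumption using a pattern mixture approach".

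Section 5.0, Objective 2, motivates the objective by a "documented relationship between Caregiver burden, stress, strain and quality of life and the ability for the care-recipient to remain in the home".

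**The concern.** Each rule lets a p-value decide something that should be fixed beforehand.

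The kurtosis rule can change the outcome from a score to a yes/no variable. The statistic does not measure what the rule is for, and its result depends on how many caregivers happen to be surveyed. The power table in section 7.0 is for a continuous score and does not carry over to a dichotomy at an unknown cut.

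The missing-data rule is introduced to avoid bias from analysing completers only, yet one of its branches is exactly that analysis. Similar baseline scores do not show that later loss is unrelated to outcome. The plan itself ties caregiver strain to whether the Veteran can stay at home, so outcome-related loss is plausible. The only named method that addresses such loss has no trigger. A completers-only result could therefore be reported as the program effect with no check on this assumption.

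**Working it through.** **1. The plan's power figure.** Inputs from the Power paragraph of section 7.0: SD 10, 55 controls, about 1,000 VD-HCBS caregivers, 4 points. Two-sided 5% is assumed, since no level is stated.

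SE = 10 × √(1/55 + 1/1,000) = 1.385. Power = Φ(4/1.385 − 1.96) = Φ(0.928) = 82.3%, against 82% stated. All twelve cells of the table reproduce within one percentage point. The figure is right for the continuous score; 4 points is 0.4 SD.

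**2. What the kurtosis test responds to.** It is taken as an upper-tail test with z above 1.96, my assumption.
- *Spread.* A score confined to five adjacent, equally likely values has excess kurtosis −1.2 × (26/24) = −1.3, so it is not flagged despite its narrow range. A skewed score filling 0–30 (rounded gamma, shape 2, mean 8) is flagged in about 100% of samples at n = 1,000 if left untransformed. After a square-root or log(x+1) transformation it is flagged in under 1% at n = 500 to 2,000.
- *Sample size.* A t distribution with 16 df has excess kurtosis 6/(16 − 4) = 0.5. It is flagged in about 10/43/67/90% of samples at n = 66/500/1,000/2,000. Because it is symmetric, transformations aimed at skewness do not help.

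**3. Cost of the split.** Split at the control median, so p1 = 0.5 and p2 = F(0.4 × SD). For t with 16 df, SD = √(16/14) = 1.069 and p2 = F(0.428) = 0.663.
- Pooled proportion (55 × 0.5 + 1,000 × 0.663)/1,055 = 0.654.
- SE under no difference: √(0.654 × 0.346 × (1/55 + 1/1,000)) = 0.0659.
- SE under the alternative: √(0.25/55 + 0.663 × 0.337/1,000) = 0.0691.
- Power = Φ((0.163 − 1.96 × 0.0659)/0.0691) ≈ Φ(0.49) ≈ 69%.

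| Shape | p2 | Power, median split |
|---|---|---|
| t, 16 df | 0.663 | 69% |
| t, 10 df | 0.668 | 71% |
| t, 5 df | 0.686 | 80% |
| Laplace | 0.716 | 91% |

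The cut matters too: for t with 10 df, cuts leaving 25% or 10% of controls above them give 63% or 35%.

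**4. What the baseline gate can see.** It uses baseline scores only. If loss is unrelated to them, k independent tests at 5% are all non-significant with probability 0.95^k: 77% for k = 5 and 46% for k = 15. In simulations (5 or 15 baseline variables, 500 or 1,000 caregivers, 20–24% loss), the gate led to completers only in 63–82% of runs when loss followed the part of the follow-up score unrelated to baseline. It did so in 0.4–30% when loss followed the follow-up score itself. Completers-only is thus chosen most often where the loss is least visible at baseline.

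**5. Whether the imputation branch would repair it.** The section 7.0 model adjusts for baseline values. Assumptions: SD 10, baseline/follow-up correlation 0.5, 1,000 VD-HCBS caregivers, VD-HCBS loss of 20% or 24%, no control loss. Matching was not simulated, although the plan says "we will use matching with replacement in which controls can be used multiple times". Bias in the adjusted group difference, in points:

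| Loss depends on | Completers (20% / 24%) | Imputed from baseline (20% / 24%) |
|---|---|---|
| follow-up score | 0.70 / 1.20 | 0.71 / 1.20 |
| part of follow-up unrelated to baseline | 0.84 / 1.37 | 0.84 / 1.38 |
| baseline only | −0.01 / 0.00 | −0.01 / 0.01 |

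The columns agree because outcomes imputed from baseline follow the same regression that the completers already determine. The sizes follow from the assumed loss and are not estimates for this study; only the agreement is the result.

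**The case against.** Four things can be said on the other side.

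*Transformation comes first.* It appears earlier in the paragraph, and it removes nearly all flags for a skewed score. That stands, and it narrows the first rule to scores that stay heavy-tailed after transformation, chiefly symmetric ones. But the text does not say that the kurtosis test is applied to transformed scores.

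*A binary model is available.* Proportional odds with two categories is logistic regression. That also stands; the real gap is the cut. A reader might infer that the cut would be picked to suit the result, inflating false positives. The documents do not support this: the distribution checks are placed before any testing for change.

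*The model adjusts for baseline, so completers-only loses little against imputation.* Step 5 confirms it. A reader might infer that making imputation primary would remove the bias. It would not, when it draws on baseline alone. Loss that depends only on measured baseline values is already handled by the adjustment.

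*The plan only looks for indications of missingness completely at random, and the pattern-mixture sentence could cover both branches.* Both are fair readings. Yet the baseline comparison still selects the analysis, and on either reading the sensitivity analysis is discretionary with no stated trigger.

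**Conclusion.** The point holds as a fault in two decision rules, and it should be corrected before analysis. It does not show that the Objective 2 result will be biased.

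The kurtosis rule is poorly matched to its aim and depends on sample size. For mildly heavy-tailed symmetric scores a median split costs 11 to 13 percentage points of power (about 82% to 69–71%). It would be wrong to infer that dichotomising always costs power: the loss is about 2 points for t with 5 df, and very peaked shapes gain. The documents give an SD for one scale and no distributions, so which scores would be flagged cannot be predicted.

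The missing-data rule leaves the completers-only branch without a required check against loss driven by events after baseline. A reader might go on to infer a bias of known size or sign in the group comparison. The documents give no Objective 2 drop-out rate or mechanism, so neither can be derived. The Recruitment Methods text for Objective 2 describes the controls as having both surveys, so the gate mainly concerns VD-HCBS caregivers.

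**What to change.** 1. Delete the kurtosis-to-dichotomy rule. Analyse financial strain, CESD-10, burden and positive aspects as continuous scores with the linear model already in section 7.0. Keep any dichotomy secondary, with its cut fixed in advance.
2. Report the completer/drop-out baseline comparison descriptively. Fix one missing-data method beforehand and use it whatever that comparison shows.
3. Remove the condition on the pattern-mixture analysis and always run it. Use separate shifts for caregivers whose Veteran left VD-HCBS and for survey non-response, and report the shift at which the conclusion changes.

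The linear model, multiple imputation and the pattern-mixture approach are all already named. The cost is revised SAP wording plus modest extra programming and reporting. The gain is an outcome scale that no longer hangs on a kurtosis test, and a stated limit on how far outcome-related loss could go before the conclusion fails. The change does not itself remove bias from such loss.

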## Recruitment Methods:

This objective will be completed in two separate stages. The first stage will be data collection of caregiver Survey data via telephone surveys. Caregivers of Veterans receiving VD-HCBS will be given a sealed packet during the ADNA's initial visit or will be placed within the Veteran interview packet to be mailed as described above. The sealed packet will be labeled "To the Veteran Caregiver" and will include information about the project, the phone survey, the goal of the project, and provide contact information of a Providence-based project staff member to address any questions or concerns they may have prior to participating. Also included in these letters will be a copy of the informed consent sheet for caregivers to keep and will contain contact information should they have any questions either before or after the survey. In addition, within this introductory packet will be an opt-in postcard that caregivers will be asked to complete and return if they wish to participate or be contacted again regarding this study. A draft of this opt-in postcard is included in the application (Opt-in Postcard included in submission). . Data for the outcomes for caregivers of Veterans enrolled in the VD-HCBS program will be obtained from the VHA Office of Geriatrics and Extended care following an approved Data Use Agreement in accordance with VA Policy. We estimate that there will be approximately 4500 Caregivers' data included in this data set. Data for the control group will be obtained from the VHA Caregiver Support Program following an approved Data Use Agreement in accordance with VA Policy. We estimate that there will be approximately 158 Caregivers (92 approved for the Caregiver Support Program and 66 not approved) with pre and post survey data included in this data set.

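### Objective 2 selects the two caregiver groups differently after baseline: a Veteran's exit from VD-HCBS counts as missing follow-up, while controls are described as having both surveys

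*Combined protocol and SAP*

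**What the plan says.** Section 7.0, Objective 2, gives two reasons for missing follow-up in the VD-HCBS group. The first is that the Veteran "is no longer receiving VD-HCBS at the 6-month follow-up period". The second is that "a Caregiver participant is lost to follow-up because of non-participation".

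Baseline scores of completers and dropouts are then compared. If no significant difference is found, "then we will proceed with data analysis of the Caregivers who completed both rounds of the survey". Otherwise, "if we determine that the data are missing at random, then we will impute the missing data using a multiple imputation technique". A further step applies only if judged necessary, and no trigger is given: "we will perform sensitivity analysis to examine the plausibility of the missing at random assumption using a pattern mixture approach".

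The control data already exist. Section 5.0, Objective 2, Recruitment Methods, describes about 158 VA CARES caregivers (92 approved, 66 not approved) "with pre and post survey data included in this data set". Section 7.0 takes the 66 non-approved caregivers as the control group. The documents give no VA CARES baseline count, no attrition figure and no missing-data rule for controls.

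On timing, Section 5.0, Objective 2, says "Each Caregiver will participate in two 20-minute phone surveys held 12 months apart", whereas the missing-data paragraph of Section 7.0 places follow-up at 6 months.

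**The concern.** Exit from the program happens after baseline and may be related to how the caregiver is faring. Section 5.0 itself links caregiver burden and strain to the Veteran's ability to stay at home, and places caregivers on the causal chain of the program's effect. Leaving out caregivers whose Veteran has left, or imputing their outcomes from those whose Veteran stayed, conditions on something the program may influence.

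The control group is formed by another route: caregivers are present because they answered twice. Propensity matching on baseline variables cannot balance two groups that were filtered differently after baseline.

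At stake is what the estimate means. Objective 2 asks about the effect of VD-HCBS on caregivers. A completers-only comparison would describe caregivers whose Veteran stayed and who answered again, set against controls who answered again.

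**Working it through.** **1. The plan's own figure.** Section 7.0 (Power) uses SD 10, 55 controls with the Positive Aspects of Caregiving score, and about 1,000 VD-HCBS caregivers. Alpha is not stated; two-sided 0.05 is assumed.

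- SE = 10 × √(1/55 + 1/1000) = 1.38 points.
- Power for a 4-point difference = 82.3%, against 82% in the plan's table. All 12 cells of the table reproduce to within 1 percentage point.

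**2. Effect of exit on power.** Losing 10, 20, 30 or 40% of the 1,000 VD-HCBS caregivers gives 82.1, 81.8, 81.5 or 81.0% power for 4 points. Precision is set by the 55 controls, so the issue is bias, not power.

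**3. Completers-only bias in one group.** Let d be the share lost and g the mean change in stayers minus that in leavers. The full-cohort mean is (1 − d) × stayers + d × leavers, so stayers exceed it by d × g. The documents give neither d nor g. The values below are assumptions, and the false-positive rates use the SE from step 1.

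| d | g (points) | d × g (points) | False-positive rate at nominal 5% |
|---|---|---|---|
| 20% | 5 | 1.0 | 11% |
| 30% | 5 | 1.5 | 19% |
| 20% | 10 | 2.0 | 30% |
| 30% | 10 | 3.0 | 58% |

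Over d = 10 to 40% and g = 2.5 to 10, d × g runs from 0.25 to 4.0 points. The upper end needs a gap of one full SD.

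**4. Both groups together.** Controls may also have been lost before their post survey. Net bias = d × g (VD-HCBS) − d × g (controls). With 20% and 5 points on the VD-HCBS side:

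- no control loss: 1.0 − 0 = +1.0;
- control loss of 20% with a 5-point gap: 1.0 − 1.0 = 0;
- control loss of 20% with a 10-point gap: 1.0 − 2.0 = −1.0.

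The sign depends on figures that the documents do not contain.

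**5. Does the planned baseline check protect?** It was simulated with 4,000 runs per setting, 1,000 VD-HCBS caregivers, 55 controls, SD 10 and no true effect among all starters. Leaving was unrelated to baseline but related to change. The check found no significant difference in about 95% of runs, so the completers-only analysis would have followed. Biases were 1.0, 1.5, 2.0 and 3.0 points and false-positive rates 11, 20, 30 and 57% for the four rows above. The 95% follows from the set-up. It shows what the check cannot see, not how often this happens.

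**6. The two analysis branches side by side.**

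- Completers only: VD-HCBS caregivers are selected on the Veteran staying and on answering; controls on answering alone.
- Multiple imputation: VD-HCBS is restored to its baseline cohort, but controls remain those with both surveys. If leavers have no observed follow-up, their values must be borrowed from stayers under an assumption the data cannot test.

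**The case against.** The plan says that data may be missing for these reasons. It sets no rule to stop calling or to discard a caregiver whose Veteran leaves, and Section 5.0 gives each caregiver two surveys without requiring continued enrolment. So the sponsor may already intend to call everyone. This stands in part, but listing exit apart from non-participation implies that exit alone can remove a follow-up, and the text should settle it.

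The plan also states the aim of avoiding bias from analysing completers only, and it names imputation and pattern mixture analysis. Baseline strain, depressive symptoms and burden are measured, so exit driven by baseline strain could be detected and adjusted for. That is fair. What remains is exit related to later change, a significance test used as a gate, and a sensitivity analysis with no trigger.

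The estimand can be read more than one way: the Objective 2 hypothesis speaks of caregivers of participating Veterans, so an effect among stayers is defensible. The plan would need to say so, and the different selection of controls would remain.

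A reader might infer that the bias favours the program. The documents do not support that. Control completers may look too well if strained controls dropped out, and a Veteran's exit could relieve some caregivers. A reader might also infer that the controls are fully complete. Only 55 of the 66 have the Positive Aspects score, so completeness is described at survey level only. Nor do the documents say how VA CARES handled a Veteran's death or placement.

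**Conclusion.** The point holds as a difference in post-baseline selection between the groups that the planned methods do not remove. It is a validity problem; the power table is not in error.

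Size and direction cannot be determined from the documents. The illustrative 0.25 to 4.0 points rest on assumed exit rates and gaps. They cover only VD-HCBS loss under the completers-only branch and use the SD of one scale, so they should not be quoted as an expected share of the 4-point design difference. That exit is related to outcome is plausible on the plan's own account of caregiver strain and remaining at home, but it is not shown.

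The follow-up interval is stated in two ways. Because cumulative exit depends on the interval, the two statements must be reconciled.

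**What to change.** 1. Attempt the second survey with every baseline caregiver, whether or not the Veteran is still in VD-HCBS. Record exits by reason, including death, and state how the caregiving scales are handled after a death.
2. Make analysis by VD-HCBS entry the main comparison and stayers-only secondary.
3. Do not let a non-significant baseline test trigger the completers-only analysis.
4. Make the pattern mixture sensitivity analysis mandatory.
5. Ask for VA CARES baseline records without a post survey, and apply the same missing-data method to both groups. If they cannot be obtained, say so and report a like-for-like sensitivity analysis: all VD-HCBS caregivers who answered the second survey, whatever the Veteran's program status, against controls who answered theirs.
6. Reconcile the 6-month and 12-month follow-up statements.

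The cost is some extra 20-minute calls within the planned telephone survey and one added data request. The documents do not show that the additional VA CARES records exist or can be released, so the last part of item 5 may be what is reported.
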